With the current study design, all participants will have a screening period of up to 30 days. During that time, a single baseline image of the EZ lesion will be taken to establish eligibility and the study baseline. The EZ line break area for eligibility will be determined by the reading center. Images will be reviewed for quality and may be repeated if necessary and obtained within the screening period (30 days). Two independent masked readers will determine lesion area from a single acceptable image. If the 2 estimates of area are within 10% and at least 1 measure is ≥ 0.16 and ≤ 2.0 mm², the MacTel lesion will be deemed eligible. If the 2 readings differ by more than 10%, an arbitrating reader will estimate the area. If the third reading is within 10% of either of the first 2 estimates, then the third and selected primary readings will be used to establish eligibility. Baseline EZ area will be the mean of the 2 qualifying estimates.

The implant surgery/sham procedure in the study eye should be completed within 30 days of randomization and/or up to 58 days from screening. Only 1 study-eligible eye of each participant will be designated as the study eye. Participants will be randomized (1:1) to receive the NT-501 implant or to undergo the sham procedure in the study-eligible eye. The implant surgery/sham procedure will occur on Day 0. Participants will be assessed on Day 1, Week 1 (± 2 days), Month 1 (± 7 days), Month 3 (± 14 days), Month 6 (± 30 days), Month 12 (± 30 days), Month 16 (± 30 days), Month 20 (± 30 days), and Month 24 (± 30 days). Note that, in regions other than France, a telephone contact will be made at Month 1 (± 7 days) and Month 3 (± 14 days) instead of a clinic visit. A subset of participants, based on the date of the surgical procedure, will be assessed at Month 36 (± 30 days) and Month 48 (± 30 days). Upon completion of the 24, 36, or 48-month observation, all participants will be followed for safety and disease progression in a nested substudy of the existing Natural History and Observation and Registry Study of Macular Telangiectasia Type 2 (NHOR)²⁰.

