5 SAMPLE SIZE CONSIDERATIONS

Sample size calculation is based on the comparison of the 2 groups over 24 months (720 days) incorporating a longitudinal mixed effects model. The number of participants, N, in each of the 2 groups [15] is calculated as follows: We assume that, in the NT-501 implant group, the response of change in EZ area is as follows:

$$Y_{ij} = \beta_{0NT-501} + \beta_{1NT-501}x_{ij} + \varepsilon_{ij}, \quad j = 1, \dots, n; i = 1, \dots, m$$

For the sham group the sham equation holds as follows:

$$Y_{ij} = \beta_{0sham} + \beta_{1sham}x_{ij} + \varepsilon_{ij}, \quad j = 1, \dots, n; i = 1, \dots, m$$

Both groups have the same number of participants (m), $x_{ij} = x_j$ represents the duration between the first and the jth visit in which case β_{1sham} and $\beta_{1NT-501}$ represents the rates of change in Y for Sham and NT-501 implant, respectively, and each person is measured at the same time points, and each participant has n repeated observations of EZ area planned to occur at baseline, 12, 16, 20 and 24 months (where months will be converted to years).

The number of participants, m, in each of the 2 groups [15] is calculated as follows:

$$m = \frac{2(z_{\alpha} + z_{\beta})^2 \sigma^2 (1 - \rho)}{ns_x^2 d^2}$$

where $d = \beta_{1sham} - \beta_{1NT-501}$ and s_x^2 is the within-subject variance of x_j .

Using the above equation with a Type 1 error rate of 0.05 (2-sided); variance of endpoint (σ^2)= 0.0256; correlation between within participant observations (ρ) = 0.6; $s_x^2 = 0.47$ and n = 5 (baseline and 12, 16, 20 and 24 months) we have 80% power with a sample size of 50 participants per treatment group to detect a difference in rate of change 0.037 mm²/year in the EZ area in the NT-501 implant group versus the sham group. The sample size will be increased to 56 participants per treatment group (112 total participants) to provide adequate power in the analysis of the population evaluable for efficacy.

The statistical model will be a random intercept model as follows:

$$Y_{ij} = (\beta_0 + b_{0i}) + \beta_1 * TRT + \beta_2 * TIME + \beta_3 * TRT * TIME + \varepsilon_{ij}$$

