7.4 Covariates and Subgroups

There are no plans to adjust the primary efficacy analysis for baseline characteristics and disease status. Exploratory analyses will be conducted to assess the potential contribution of baseline disease characteristics on the likelihood of a response to treatment.

Exploratory analyses will be performed to assess the potential impact of various prognostic factors on efficacy. Appropriate statistical models will be fit with these factors as covariates and the effect of treatment will be assessed after adjusting for other significant risk factors. Risk factors will include, but are not limited to age, gender, region, and baseline EZ area.

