9 EFFICACY EVALUATION

9.1 Primary Efficacy Analysis

The primary hypothesis is that the NT-501 implant will slow the rate of change in the EZ (IS/OS) area loss. The primary efficacy endpoint will be analyzed using the mITT Population but restricted to only those participants with at least 3 visits recorded: Baseline, Month 24, and at least one of Month 12, 16, or 20 visits. An analysis will also be conducted with the PP Population with the same restriction to only participants with at least 3 visits recorded: Baseline, Month 24, and at least one of Month 12, 16, or 20 visits.

The primary efficacy variable will be the rate of change that will be determined by using values from the EZ area as measured by SD-OCT. EZ area will be defined as the mean of 2 independent readings of the single eligible SD-OCT enface image taken at Baseline and at Months 12, 16, 20, and 24. A longitudinal mixed model will include EZ area as the dependent variable, a random intercept term to account for within subject variability, treatment group, time as a continuous variable, and the interaction between treatment and time. Time will be captured as the relative study day of the respective efficacy assessment and will include the days corresponding to the Baseline, Month 12, 16, 20, and 24 visits. The difference in the rate of change in EZ area over 24 months will be computed by including Baseline, Months 12, 16, 20, and 24 EZ measurements, will be compared using a random intercept model and the corresponding 95% confidence interval (CI), SE, test statistic, and 2-sided p-value of the difference between treatment group parameters by computing the parameter estimate for the treatment by time interaction term. An unstructured covariance structure will be implemented as with continuous time there will be a single parameter each for between and within participant variability.

Prior to the analysis, out of window visits will be incorporated as noted in Section 7.5. With a mixed effects model as the primary analysis model, no imputation of missing data will be done.

As stated in Section 7.6, it may be determined prior to study end and database lock that the most appropriate parameterization of time is as a categorical variable. If this occurs, the modification to the

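### The primary slope model gives each arm its own intercept and so leaves unused the equal expected baseline EZ area that randomization provides, which costs about 10 power points at the plan's ρ of 0.6 and less if ρ is higher

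*SAP*

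**What the plan says.** The default primary model is in SAP 9.1 and Protocol 12.3.1: "A longitudinal mixed model will include EZ area as the dependent variable, a random intercept term to account for within subject variability, treatment group", continuous time, and their interaction. The equation in SAP 5 and Protocol 12.2 has the same terms. EZ area at Baseline and Months 12, 16, 20 and 24 forms the response, and the test is on the interaction coefficient.

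On baseline, Protocol 4.1 says that "a single baseline image of the EZ lesion will be taken to establish eligibility and the study baseline". Protocol 7.2.1 requires screening results to be reviewed and eligibility settled before randomization, which is 1:1.

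On adjustment, SAP 7.4 says: "There are no plans to adjust the primary efficacy analysis for baseline characteristics and disease status". Baseline EZ area enters as a covariate only in a sensitivity analysis (SAP 9.1.1).

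On power, SAP 5 uses σ² = 0.0256 and a "correlation between within participant observations (ρ) = 0.6", and concludes: "we have 80% power with a sample size of 50 participants per treatment group to detect a difference in rate of change 0.037 mm²/year". Enrolment is then raised to 56 per arm. SAP 5.1.1 adds that, when the Phase 2 eyes are treated as independent, both the variance and ρ come out higher (ρ markedly so) with power a little above 80%, and that this trial is assumed to resemble that case. It prints no value for that ρ.

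**The concern.** The treatment main effect lets the arms differ in expected EZ area at time zero. The baseline scan precedes allocation, so among all randomized participants that difference is zero in expectation and any observed gap is chance. Estimating it anyway spends information. Under a random-intercept model with complete visits, the planned estimator reduces to the contrast of within-eye slopes. It ignores what the level of the later scans says about treatment once both arms are known to start from the same mean.

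A constrained longitudinal model has one common baseline mean and no treatment main effect. It tests the same interaction on the same scans with a smaller standard error. At stake is precision that could be had without further patients or visits, in a trial of 112 participants sized for 80% power.

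**Working it through.** **Inputs** (SAP 5): two-sided α = 0.05, σ² = 0.0256, ρ = 0.6, d = 0.037 mm²/year, and visits at x = 0, 1, 1.333, 1.667 and 2 years. So the within-eye variance is σ²(1−ρ) = 0.01024, the mean of x is 1.2, and Sxx = 1.44 + 0.04 + 0.0178 + 0.2178 + 0.64 = 2.356. Then s_x² = 2.356/5 = 0.471, which matches the plan's 0.47.

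**1. The plan's figure.** m = 2(1.960 + 0.842)² × 0.01024 / (5 × 0.47 × 0.037²) = 49.97, so 50 per arm. It reproduces.

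**2. Planned model, separate intercepts.** SE = √[2 × 0.01024 / (50 × 2.356)] = 0.01319. Power = Φ(0.037/0.01319 − 1.96) = 80.1%.

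**3. Common baseline mean.** In units of 1/σ², the within-eye slope information is A = Sxx/(1−ρ) = 2.356/0.4 = 5.889. The constraint adds B = n·x̄²/[1 + (n−1)ρ] = 7.2/3.4 = 2.118. The variance ratio is A/(A+B) = 0.736, so SE = 0.01319 × √0.736 = 0.01131.

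| Per arm | Planned model | Common baseline mean | Gain (points) |
|---|---|---|---|
| 50 | 80.1% | 90.5% | 10.4 |
| 56 | 84.4% | 93.4% | 9.0 |

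About 37 per arm (50 × 0.736) would then give 80%. A simulation of 20,000 trials at 50 per arm gave power of 79.8% and 90.5%, with null rejection of 4.9% and 5.0%. It used known variances and no variation in true slopes.

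**4. Dependence on ρ.** SAP 5.1.1 reports a higher variance and a higher ρ with little change in power, so it is reasonable to hold σ²(1−ρ) at 0.01024. Planned power then stays at 80.1% at 50 per arm.

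| ρ | Power with common baseline mean | Gain (points) |
|---|---|---|
| 0.6 | 90.5% | 10.4 |
| 0.7 | 87.8% | 7.7 |
| 0.8 | 85.2% | 5.0 |
| 0.9 | 82.6% | 2.5 |
| 0.95 | 81.3% | 1.2 |

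The plan's σ² implies a total SD of 0.16 mm², which looks small beside an eligibility range of 0.16 to 2.00 mm². If the total SD were 0.3 to 0.5 mm² (an assumption), ρ would be about 0.89 to 0.96 and the gain about 3 to 1 points.

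**5. What the baseline scan already contributes.** Removing it from the planned model cuts power at 50 per arm to 27.5%.

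**6. Unequal expected baselines in the analysed set.** Suppose the analysed arms differ by a persistent 0.05 mm² (an assumption). The planned slope contrast is unaffected. The constrained one is biased by (0.05/1.2) × B/(A+B). At ρ = 0.6 that is 0.0417 × 0.2645 = 0.011 mm²/year, or 30% of d. At ρ = 0.9, B/(A+B) = 1.565/(23.556 + 1.565) = 0.062 and the bias is 0.0026.

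**7. Variation in true slopes.** Take a slope SD of 0.05 mm²/year (an assumption), ρ = 0.6 and 50 per arm. A random-intercept fit absorbs the extra variance as a within-eye variance of 0.01024 + 2.356 × 0.0025/4 = 0.01171.
- Planned model: reported SE = √[2 × 0.01171/(50 × 2.356)] = 0.0141. True SE = √[2(0.01024/2.356 + 0.0025)/50] = 0.0166. Null rejection = 2Φ(−1.96 × 0.0141/0.0166), about 9.5%.
- Common baseline mean: the same calculation gives about 11.4%. Simulation puts the pair at about 10% and 12% to 13%.
- With a slope SD of 0.03 the large-sample figures are 6.7% and 7.5%. If the model includes a matching random slope, power at that SD is 72.4% with separate intercepts and 82.4% with a common baseline mean.

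**The case against.** **The planned model is valid as it stands.** Its formula matches its analysis, the 80% is right, and declining baseline adjustment is stated openly. This holds. The point is one of efficiency only.

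**The 10-point figure relies on ρ = 0.6.** SAP 5.1.1 suggests that the one-eye design has a higher value. This also holds, and it is why the size has to be given as a range.

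**Equal expected baselines are not guaranteed in the analysed set.** The primary analysis is limited to operated participants with Baseline, Month 24 and at least one of Months 12, 16 and 20, and that selection happens after randomization. Step 6 shows that the planned model is immune to a persistent gap and the constrained one is not. This is the strongest reason to keep the planned model alongside.

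**The change is not purely one deleted term.** The plan counts days from surgery, and the scan may precede surgery by up to 58 days. Dropping the main effect alone would place the common mean at surgery and let the treatment effect run before implantation. A random-intercept-only fit would also worsen the inflation in step 7. Both objections stand and are met in the fix.

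**The covariate-adjusted sensitivity analysis might seem to cover this already.** It does not. With complete, balanced visits, a baseline covariate entered only as a main effect leaves the random-intercept slope contrast unchanged.

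**Conclusion.** The point holds as a cheap improvement. The primary model does not use the equality of expected baselines. On the plan's own inputs this forgoes about 10 power points at 50 per arm and 9 at 56. If ρ is 0.8 to 0.95, the gain at 50 per arm is about 5 points down to 1. These figures assume complete visits, an exchangeable correlation, no variation in true slopes, and equal expected baselines in the analysed set.

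Three stronger readings are tempting and are not supported:
- A reader might infer that the baseline scan does nothing for the slope comparison. It is one of the five responses and supplies most of the slope information (step 5).
- A reader might infer that the stated power is wrong. It reproduces for the planned model.
- A reader might take 10 points as the loss in this trial. That needs ρ = 0.6, and SAP 5.1.1 points higher.

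**What to change.** Before database lock, in SAP 9.1 and Protocol 12.3.1 (and the matching equations in SAP 5 and Protocol 12.2):

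1. Remove the treatment main effect so that both arms share one mean at the pre-randomization scan.
2. Code the treatment-by-time term as 0 at that scan, since study day is counted from surgery. Test that term as now.
3. Use a robust (sandwich) SE clustered on participant, or add a random slope, so that variation in true slopes does not inflate type I error.
4. Keep the planned separate-intercept model as a named sensitivity analysis, to show whether the restriction to participants with Month 24 data has disturbed the equal-baseline condition.
5. Amend SAP 7.4, and the same statement in Protocol 12.1, to say that the primary analysis uses baseline EZ area through a common baseline mean.

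The cost is a short amendment and some programming. It needs no new data, and the endpoint and hypothesis do not change. The downside is a small reliance on equal expected baselines in the analysed set, which item 4 checks.

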9.2 Secondary Efficacy Analysis

The secondary endpoints will be analyzed using the mITT Population and the PP Population to test for superiority of NT-501 implant over sham. The secondary endpoints are listed below:

- Mean change in aggregate sensitivity of microperimetry within the EZ line break area from the Baseline Visit to the Month 24 Visit
- Mean change in reading speed from the Baseline Visit to the Month 24 Visit
- Mean change in the National Eye Institute Visual Function Questionnaire-25 (NEI-VFQ-25) near activities subscale score from the Baseline Visit to the Month 24 Visit

The observed change from Baseline visit to the Month-24 visit will be compared using t-tests. The analyses will be based on the actual values observed at the Baseline and the Month-24 visit efficacy assessment, regardless of timing of the visit as long as it occurs within +/- 30 days for pre-COVID period or within +119 days post-visit timepoint for COVID-related delays. The estimated mean treatment effect, a 95% confidence interval (CI), and a 2-sided p-value will be provided. No imputation of missing data will be done.

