1. INTRODUCTION AND RATIONALE

1.1 BACKGROUND

Idiopathic macular telangiectasia type 2 (MacTel) is a bilateral neuro/vascular/glia degenerative condition of unknown etiology with characteristic neurosensory atrophy and perifoveal telangiectatic vessels that leak on fluorescein angiography¹. Other characteristic lesions include loss of retinal transparency, crystalline deposits, a decrease or absence of macular pigment, and hyperplasia of the retinal pigment epithelium (RPE) in the macular area. Spectral-domain optical coherence tomography (SD-OCT) assessments show disruption of the photoreceptor inner segment/outer segment junction line (IS/OS line) or ellipsoid zone (EZ)², and hyporeflective cavities in both the inner and outer retina.

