6. STUDY CONDUCT

All participants will have a screening period of up to 30 days. The implant surgery/sham procedure in the study eye should be completed within 30 days of randomization and/or up to 58 days from screening. Only 1 study-eligible eye per participant will be allowed in this study. Participants with 1 study eye that meets the inclusion criteria will be randomized (1:1) to receive the NT-501 implant or sham procedure in the study-eligible eye. If both eyes qualify for the study, the study eye will be chosen as part of the centralized randomization process. The eye will be deemed eligible only after the reading center has reviewed all baseline images.

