12.3.2 Secondary Endpoint(s)

The secondary endpoints will be analyzed using the mITT population and the PP population to test for superiority of NT-501 over sham. The secondary endpoints are listed below:

- Mean change in aggregate sensitivity of microperimetry within the EZ line break area through 24 months
- Mean change in reading speed from baseline through 24 months
- Mean change in the NEI-VFQ-25 near activities subscale score from baseline through 24 months

Continuous secondary outcomes will be analyzed using a longitudinal mixed effects model and the corresponding 95% CI, SE, test statistic, and p-value of the difference between treatment group means at the 24-month time point will be computed. For the mixed effects model, fixed effects will include the treatment group (between-participant factor) and the visit (within-participant factor). The unstructured covariance matrix is preferred for this analysis. If the model does not converge, the “best” covariance structure will be chosen based on Akaike’s Information Criteria²³.

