4.4 Efficacy and Safety Variables

4.4.1 Efficacy Variables

The efficacy variables in this study include EZ area (i.e., area of IS/OS loss) measured by SD-OCT, retinal sensitivity measured by Macular Integrity Assessment (MAIA) microperimetry, reading speed using the International Reading Speed Texts (IReST) Worksheets developed by the IReST Study Group [14], and participant responses to the NEI-VFQ-25 questionnaire, which is described below.

International Reading Speed Texts (IReST)

The International Reading Speed Texts (IReST) consists of paragraphs of text (approx. 130 words per text) - according to the everyday life reading demands with the same difficulty, content and linguistic characteristics in the different languages. It consists of a set of ten equivalent texts in each language for repeated measurements and international studies and was already evaluated in 425 normal young

subjects. Reading speed is calculated as the number of words read per minute.

Visual Function Questionnaire-25

The Visual Function Questionnaire-25 (VFQ-25) is a reliable 25-item version of the 51-item National Eye Institute Visual Function Questionnaire (NEI-VFQ). The survey measures health-related quality of life relevant to participants with vision disorders. The test is designed to capture the influence of vision on emotional well-being and social functioning dimensions. Response category for each item ranges from either 1 to 5 or 1 to 6. Each item will then convert to a 0 to 100 scale so that the lowest and highest possible scores are set at 0 and 100 points, respectively. In this format scores represent the achieved percentage of the total possible score (e.g., a score of 50 represents 50% of the highest possible score). Then, items within each sub-scale are averaged together to create the 12 sub-scale scores. The following table indicates which items contribute to each specific sub-scale. Items that are left blank (missing data) are not considered when calculating the scale scores. Sub-scales with at least one item answered can be used to generate a sub-scale score. Hence, scores represent the average for all items in the sub-scale that the respondent answered.

Scoring Key

Item Number	Response Category	Conversion (scores)
1, 3, 4, 15c	1	100
	2	75
	3	50
	4	25
	5	0
2	1	100
	2	80
	3	60
	4	40
	5	20
	6	0

Item Number	Response Category	Conversion (scores)
5, 6, 7, 8, 9,10, 11, 12, 13, 14,16, 16a	1	100
	2	75
	3	50
	4	25
	5	0
	6	Missing

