14.2 Appendix B: Overview of Planned Efficacy Analysis

Efficacy Endpoint		Endpoint Type¹	Population	Analysis Period	Subgroup Analysis	Sensitivity Analysis	Figure	Analysis Model
OCT	Rate of change in EZ Area Loss	1 ¹	FAS, PPS	24	Yes ²	Yes	Yes	Random Intercept Model
Microperimetry	Aggregate Sensitivity	2 ²	FAS, PPS	24	Yes ²	Yes ³	Yes	MMRM
IREST	Reading speed (words/min)	2 ²	FAS, PPS	24	Yes ²	Yes ³	Yes	MMRM
NEI-VFQ-25	Near activities subscale score	2 ²	FAS, PPS	24	Yes ²	Yes ³	Yes	MMRM

1 Indicates endpoint category, 1¹ = primary and 2² = secondary

2 Subgroup Analysis: Age at baseline, baseline endpoint measure

3 Sensitivity Analysis limited to impact of COVID-19

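### The NEI-VFQ-25 near activities test in SAP 9.2 is valid but does not adjust for the baseline score, which leaves removable variance in the last gated comparison

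*SAP*

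**What the plan says.** SAP 9.2 lists three secondary endpoints, of which near activities is the third, and gives one method for all: "The observed change from Baseline visit to the Month-24 visit will be compared using t-tests". It asks for a mean treatment effect, a 95% interval and a 2-sided p-value, and names no covariate.

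Two other places name a different method. Protocol 12.3.2 says "Continuous secondary outcomes will be analyzed using a longitudinal mixed effects model", with treatment group and visit as the fixed effects. The row for this endpoint in SAP Appendix B reads "Near activities subscale score 2 ² FAS, PPS 24 Yes ² Yes ³ Yes MMRM". Neither names the baseline score as a covariate.

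On the measure itself, SAP 4.4.1 says "The survey measures health-related quality of life relevant to participants with vision disorders". Near activities is the average of items 5, 6 and 7, with no separate version for the study eye. Protocol 1.1 says MacTel "is a bilateral neuro/vascular/glia degenerative condition of unknown etiology". Protocol 4.1 says "Only 1 study-eligible eye of each participant will be designated as the study eye", and Protocol 6 adds: "If both eyes qualify for the study, the study eye will be chosen as part of the centralized randomization process".

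Baseline enters elsewhere only in supporting roles. The Appendix B footnote reads "Subgroup Analysis: Age at baseline, baseline endpoint measure". SAP 7.4 plans exploratory covariate models with an open list of factors. The covariate-adjusted sensitivity model in SAP 9.1.1 is for the primary endpoint only, and the secondary sensitivity analyses in SAP 9.2.1 deal only with visit timing.

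**The concern.** SAP 7.8 places near activities last in the hierarchy at 2-sided 0.05. The plan states no SD, expected effect or power for it; Section 5 of the SAP sizes the trial on EZ area alone. With about 56 participants per arm and no sizing for this score, avoidable noise matters.

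A simple difference in change scores subtracts the whole baseline value, whatever its actual relation to the Month 24 value. When the correlation is below 1, this subtracts too much and carries baseline measurement noise into the outcome. Regression on the baseline score removes that excess. The baseline score is already collected, so the loss of precision is unnecessary.

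What is at stake is the width of the interval and the power of one secondary test. Type I error, the primary analysis and the two earlier secondary tests are not affected.

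**Working it through.** **The plan's own figure.** The only sample size in the documents is for the EZ area slope (Protocol 12.2, SAP 5). With σ²=0.0256, ρ=0.6, n=5, s_x²=0.47 and d=0.037, m = 2 × (1.960+0.842)² × 0.0256 × 0.4 / (5 × 0.47 × 0.037²) = 49.97, so 50 per arm as stated. There is no corresponding figure for near activities. The ρ=0.6 belongs to EZ area and cannot be taken as the correlation for this score.

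**Variance of the two comparisons.** Let σ² be the variance of the score at each visit (assumed equal), r the Baseline to Month 24 correlation, and m the number per arm.

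- Difference in mean change (t-test): (2/m) × 2σ²(1−r).
- Difference adjusted for baseline (ANCOVA): (2/m) × σ²(1−r²), ignoring the one degree of freedom spent on the covariate.
- Ratio, ANCOVA to t-test: (1−r²) / [2(1−r)] = (1+r)/2.

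| Assumed r | Ratio | Variance removed | t-test size per arm matching ANCOVA at 56 |
|---|---|---|---|
| 0.5 | 0.75 | 25% | 56/0.75 = 74.7 |
| 0.7 | 0.85 | 15% | 56/0.85 = 65.9 |

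The direction does not depend on equal variances. With SDs σ0 at baseline and σ1 at Month 24, the per-participant variance of change minus the ANCOVA residual variance is (σ0 − rσ1)², which is never negative.

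**What this means for power.** At 56 per arm, the difference detectable with 80% power by the t-test is (1.960+0.842) × √(2/56) = 0.53 SD of change. For a true effect of that size:

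- r=0.5: 2.802/√0.75 − 1.960 = 1.275, so power is about 90%.
- r=0.7: 2.802/√0.85 − 1.960 = 1.079, so power is about 86%.

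The effect of 0.53 SD is chosen only to set the scale; it is not in the documents.

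**Does adjustment change what is estimated?** A 4,000-run simulation at 56 per arm set the true person-level effect to 0.265 SD, half of 0.53. A baseline covariate explained 10% or 30% of the variance of change. The mean estimate was 0.265 to 0.266 by t-test and 0.265 to 0.267 by ANCOVA. Both methods estimate the same quantity; ANCOVA does so with less noise.

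**The case against.** The strongest reply is that nothing here is wrong. A change score does use baseline, by subtraction. Randomization makes the t-test unbiased for the person-level effect. Appendix B already plans a subgroup by the baseline endpoint measure, and SAP 7.4 leaves room for adjusted exploratory models. Near activities is tested formally only if the primary, microperimetry and reading speed have all succeeded. Adding ANCOVA would also put a third method beside two that already conflict.

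Most of this stands, and it keeps the point small. It does not remove the point: a subgroup table and exploratory models do not bring the baseline covariate into the gated test. The conflict between the t-test in SAP 9.2 and the mixed model in Protocol 12.3.2 and Appendix B has to be settled anyway, and the covariate can be written into whichever method is kept.

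A reader might infer something stronger: that because the disease is bilateral and one eye is treated, the t-test dilutes the study-eye effect, and that adjusting for the fellow eye would recover it. The documents do not support this. Any dilution comes from pairing a person-level score with one treated eye, which is a choice of endpoint. A baseline covariate leaves the estimate where it was, as the simulation shows. Nor can a sample size multiplier for dilution be derived, because the documents do not say what share of a study-eye effect reaches this score or in how many participants.

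**Conclusion.** The point holds as a missed gain in precision. SAP 9.2 specifies a valid, unbiased test of the person-level effect of treating one eye, but no document puts the baseline near activities score into that test as a covariate. Adjustment would reduce the variance of the comparison by 25% at r=0.5 and 15% at r=0.7. These figures rest on an assumed r, equal variances at the two visits and a linear relation between the two scores. The priority is low.

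A reader might also infer that a null result on this endpoint would be uninterpretable, because the treated eye may not be the one used for near tasks. That goes too far. Under the hierarchy, a formal null here would follow positive results on aggregate microperimetry and on monocular reading speed (Protocol 7.1). It would then mean only that a person-level benefit of treating one eye was not shown.

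**What to change.** In SAP 9.2, replace the t-test for near activities with ANCOVA of the Month 24 score (or, equivalently for the treatment effect, of the change) on treatment and baseline near activities score. If the SAP is reconciled toward Protocol 12.3.2 and Appendix B, use the MMRM with the baseline score as a covariate and the Month 24 contrast as the test. Make the three places agree. Add one sentence stating that the result is interpreted as the person-level effect of treating one eye.

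Optionally, summarize the endpoint descriptively by whether the study eye was the better, equal or worse eye at baseline. A near-function or EZ-based measure is preferable for that classification where both eyes have one. Protocol 1.1 and Section 14 say that distance acuity can be preserved despite paracentral scotomata and reduced reading. This summary would help interpretation but would not remove any dilution.

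The cost is SAP wording before database lock, plus one table if the optional summary is wanted. The baseline score is already collected. Test order and alpha do not change.
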